#### *5.5.2.2. Preparation of tremelimumab doses for administration with an IV bag*

The dose of tremelimumab for administration must be prepared by the Investigator's or site's designated IP manager using aseptic technique. Total time from needle puncture of the tremelimumab vial to the start of administration should not exceed:

- 24 hours at 2°C to 8°C (36°F to 46°F)
- 4 hours at room temperature
- A dose of 75 mg (for patients >30kg in weight) will be administered using an IV bag containing 0.9% (w/v) saline or 5% (w/v) dextrose, with a final tremelimumab concentration ranging from 0.10 to 10 mg/mL, and delivered through an IV administration set with a 0.2- or 0.22- $\mu$ m in-line filter. Add 3.8 mL (i.e., 75 mg of tremelimumab, with the dose volume rounded to the nearest tenth mL) to the IV bag. The IV bag size should be selected such that the final concentration is within 0.10 to 10 mg/mL. Mix the bag by gently inverting to ensure homogeneity of the dose in the bag.

If weight falls to  $\leq$  30 kg, weight-based dosing at 1 mg/kg Weight-based dosing (for patients  $\leq$ 30 kg) will be administered using an IV bag containing 0.9% (w/v) saline or 5% (w/v) dextrose, with a final tremelimumab concentration ranging from 0.10 to 10 mg/mL, and delivered through an IV administration set with a 0.2- or 0.22- $\mu$ m in-line filter. Appendix 2 includes an example of a weight-based dose calculation.

Standard infusion time is one hour, however if there are interruptions during infusion, the total allowed infusion time should not exceed 8 hours at room temperature.

Do not co-administer other drugs through the same infusion line.

The IV line will be flushed with a volume of IV diluent equal to the priming volume of the infusion set used after the contents of the IV bag are fully administered, or complete the infusion according to institutional policy to ensure the full dose is administered and document if the line was not flushed.

If either preparation time or infusion time exceeds the time limits a new dose must be prepared from new vials. Tremelimumab does not contain preservatives, and any unused portion must be discarded.

#### **5.5.3. Monitoring of dose administration**

Patients will be monitored during and after the infusion with assessment of vital signs at the times specified in the Study Protocol.

In the event of a  $\leq$ Grade 2 infusion-related reaction, the infusion rate of study drug may be decreased by 50% or interrupted until resolution of the event and re-initiated at 50% of the initial rate until completion of the infusion. For patients with a  $\leq$ Grade 2 infusion-related reaction, subsequent infusions may be administered at 50% of the initial rate. Acetaminophen and/or an antihistamine (e.g., diphenhydramine) or equivalent medications per institutional standard may be administered at the discretion of the investigator. If the infusion related reaction is  $\geq$ Grade 3 in severity, study drug will be discontinued. For management of patients who experience an infusion reaction, please refer to the toxicity and management guidelines in Appendix 1.

As with any antibody, allergic reactions to dose administration are possible. Appropriate drugs and medical equipment to treat acute anaphylactic reactions must be immediately available, and study personnel must be trained to recognize and treat anaphylaxis. The study site must have immediate access to emergency resuscitation teams and equipment in addition to the ability to admit patients to an intensive care unit if necessary.

#### **5.5.4. Accountability and dispensation of IMPs**

The trial medication will be sent to the investigator's site pharmacy preceded by the Regulatory Green Light. The medication is to be used exclusively in the clinical trial according to the instructions of this trial protocol.

When a drug shipment is received, the Investigator or designee will check the amount and condition of the delivery, drug expiration date, and sign the Receipt of Shipment Form provided. The Receipt of Shipment Form should be faxed or emailed to the CRO. The original form will preliminarily be retained at the site and will be collected at the next monitoring visit by the monitor and stored in the Trial Master File at CRO. A copy remains in the Investigator File at the site. In case of shipment problems the Investigator or designee shall contact the CRA as soon as possible.

For this trial a IWRS system will be used for IMP stock management, Pharmacy or PI designee properly identified in the personnel list and tasks delegation log, will get access to the web based platform to update receptions, destructions and dispensing of IMPs. The record must be continuously updated and contain the dates, quantities and compounds of drugs received, medication identification number(s), the patient identification number to whom the trial medication was dispensed, date and quantity of medication dispensed. The system includes an audit trail that allow to unequivocal identify the staff member and the field modify at any time.

#### **5.5.5. Disposition of unused investigational study drug**

Trial medication will be monitored by the CRA at the respective hospital pharmacy prior to destruction after having completed a final inventory, when applicable. Local or institutional regulations may require immediate destruction of the study drug used for

safety reasons, e.g., cytotoxicity or to maintain the storage capacity and functionality of the storage at the site. In these cases, it may be acceptable to destroy it by the research staff, including partially used and empty vials, dispensed before a monitoring inspection, if the verification of original documents of empty boxes that indicate the information of batch number and dispensing date to the patient on the label. This documentation will be verified against the quantity shipped, dispensed, returned and destroyed.

Prior to the destruction a final trial medication reconciliation statement must be completed.

Drug supplies will be destroyed according to the legal requirements in Spain.

All trial medication inventory forms must be made available for inspection by a Sponsor authorized representative or designee and regulatory agency inspectors. The Investigator is responsible for the accountability of all used and unused study supplies at the site.

## **6. TREATMENT PLAN**

The treatment consisted of initial TUR of the tumor, with multiple random biopsies of normal-appearing bladder urothelium, followed by durvalumab 1500 mg i.v. plus tremelimumab 75 mg i.v., every 4 weeks for a total of 3 doses.

Two weeks after the initiation of immunotherapy, normofractionated external-beam radiotherapy with high-energy photons will be started. Radiotherapy will be administered concurrently with immunotherapy at doses of 46 Gy to the minor pelvis and 64-66 Gy to the bladder.

Six weeks after the end of radiotherapy, ALL patients will undergo a new cystoscopy with biopsies of the tumor bed and all residual present lesions as an efficacy determination. In patients with persistent prominent inflammatory reaction at this moment, the cystoscopy can be performed 1-2 weeks later (6 to 8 weeks after the end of radiotherapy). Response is defined as an absence of invasive cancer at post immunotherapy biopsy ( $\leq$ cT1). Patients with response to immunotherapy will be candidates to bladder preservation, whereas in those with residual muscle invasive tumor the possibility of salvage radical cystectomy must be evaluated. Patients developing an isolated bladder invasive relapse during follow-up will be also possible candidates to salvage cystectomy, whereas those developing a superficial relapse in the preserved bladder will be managed with TUR and intravesical BCG.

Patients will be followed up every 3 months the first year, every 4 months the second year and every 6 months thereafter with abdomen and pelvis CT scan, Rx thorax, urine cytology. Additionally of the mandatory efficacy cystoscopy and bladder biopsy (6w post RT), other cystoscopy and bladder biopsy will be performed in case of detection abnormalities in the cytology or imaging studies. The study will be closed 2 years after the last patient inclusion.

## **Replacement of patients**

It is planned to replace those patients who interrupt the trial in advance (without having completed 12 weeks of treatment) and have not presented dose-limiting toxicity.

Patients who have not been taking durvalumab and tremelimumab for more than 21 days or who discontinue treatment with radiotherapy for more than 2 weeks will also be replaced.

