#### **4.4. Withdrawal of patients from study treatment**

An individual patient will not receive any further investigational product if any of the following occurs:

- An individual patient will not receive any further durvalumab + tremelimumab combination therapy.
- Patient will not receive tremelimumab monotherapy in any case.
- Withdrawal of consent or lost to follow-up.
- Adverse event that, in the opinion of the investigator or the sponsor, contraindicates further dosing.
- Any AE that meets criteria for discontinuation, as defined in Section 10.
- Patient is determined to have met one or more of the exclusion criteria for study participation at study entry and continuing investigational therapy might constitute a safety risk.
- Consumption of illicit drugs or other substances by the patient which, at the discretion of the investigator, may reasonably contribute to the toxicity or otherwise, interfere in some with the results.
- Pregnancy (proof of beta-HCG compatible with pregnancy, communicating pregnancy as a serious adverse event), or intent to become pregnant.
- Grade  $\geq 3$  infusion reaction.
- Request to discontinue treatment by the patient or a legal representative.
- At the specific request of the sponsor and / or research coordinators of the trial.
- Patient noncompliance that, in the opinion of the investigator or sponsor, warrants withdrawal; e.g., refusal to adhere to scheduled visits.
- Initiation of alternative anticancer therapy including another investigational agent.
- Development of a secondary malignant tumor requiring treatment.
- Confirmation of PD and investigator determination that the patient is no longer benefiting from treatment with durvalumab + tremelimumab. Patients who are permanently discontinued from further receipt of investigational product, regardless of the reason (withdrawal of consent, due to an AE, other), will be identified as having permanently discontinued treatment

Patients who are permanently discontinued from receiving investigational product will be followed for safety per Section 10 and Appendix 1, including the collection of any protocol-specified blood specimens, unless consent is withdrawn or the patient is lost to follow-up or enrolled in another clinical study. All patients will be followed for survival. Patients who decline to return to the site for evaluations will be offered follow-up by phone every 3 months as an alternative.

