#### **4.5. Withdrawal of patients from study**

Criteria for withdrawal of the study:

1. Withdrawal of informed consent
2. Death of the patient
3. Loss of follow-up

The investigator will do everything possible to keep all patients in the study unless it is considered that the most appropriate option for the patient is to interrupt his/her participation.

If a patient refuses to continue his/her participation in the study, all end-of-study evaluations should be performed if the patient accepts or can be evaluated. The date and reason for withdrawal should be recorded in the eCRF.

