### **6.1. Dose modification and toxicity management**

#### **6.1.1. Radiotherapy**

Patients who, for reasons unrelated to toxicity, discontinue radiotherapy for more than 2 weeks will be excluded from the study. In the case of interruptions of less than 2 weeks, the patient will resume treatment from the point where he was interrupted.

**A severe toxicity (G3-4) related to radiotherapy or due to combination of the RT+durvalumab/tremelimumab, RT will be suspended until recovery to G1. However, if it is toxicity unrelated to the RT, it will continue without variations.**

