#### **6.1.2. Durvalumab and tremelimumab**

Guidelines for the management of immune-mediated reactions, infusion-related reactions, and non-immune-mediated reactions for durvalumab monotherapy and durvalumab + tremelimumab are provided in the Dosing Modification and Toxicity Management Guidelines in Appendix 1. Patients should be thoroughly evaluated and appropriate efforts should be made to rule out neoplastic, infectious, metabolic, toxin, or other etiologic causes of the imAE. Serologic, immunologic, and histologic (biopsy) data, as appropriate, should be used to support an imAE diagnosis. In the absence of a clear alternative etiology, events should be considered potentially immune related.

In addition, there are certain circumstances in which durvalumab and tremelimumab should be permanently discontinued (see Section 4.4 of this protocol and the Dosing Modification and Toxicity Management Guidelines in Appendix 1).

Following the first dose of IP, subsequent administration of durvalumab and tremelimumab can be modified based on toxicities observed as described in the Dosing Modification and Toxicity Management Guidelines in Appendix 1. These guidelines have been prepared by the Sponsor to assist the Investigator in the exercise of his/her clinical judgment in treating these types of toxicities. These guidelines apply to AEs considered causally related to durvalumab monotherapy and the durvalumab + tremelimumab regimen by the reporting investigator.

**Dose reductions are not permitted.** In case of doubt, the Investigator should consult with the Study Physician. In case of severe grade 3-4 toxicity, the possibility to discontinue tremelimumab, following the administration of durvalumab alone concurrently with radiotherapy, when the toxicity will recover, should be considered.

It is planned to replace those patients who interrupt the trial in advance (without having completed 12 weeks of treatment) and have not presented dose-limiting toxicity. Patients who have not been taking durvalumab and tremelimumab for more than 21 days or who discontinue treatment with radiotherapy for more than 2 weeks will also be replaced.

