#### 11.1.2. Efficacy analysis set

The efficacy analysis will be a *per protocol analysis*. The efficacy analysis set will include all patients who receive at least 2 cycles of durvalumab and 3 weeks of radiotherapy. The efficacy analysis set will be the primary population for evaluating treatment efficacy.

Additionally, intention to treat analysis will be performed for efficacy data.

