#### 11.2.2. Efficacy analyses and exploratory analyses

Table 8. *Efficacy analyses and exploratory analyses*

Objectives	Variable	Analysis	Clinical factors	Analysis population
Primary: efficacy of durvalumab plus tremelimumab with concurrent radiotherapy in terms of pathological response rate	Pathological response rate	1. Proportion estimation with a 95% confidence interval 2. Simon two stage decision rule 3. Logistic regression with clinical factors	Tumour size Tumour localization Histology Biomarkers	Per protocol
Secondary 1a: bladder preservation.	Rate of bladder preserved	1. Proportion estimation with a 95% confidence interval 2. Logistic regression with clinical factors	Tumour size Tumour localization Histology Biomarkers	Per protocol
Secondary 1b: bladder preservation.	Rate of immediate and late salvage cystectomies.	1. Proportion estimation with a 95% confidence interval 2. Logistic regression with clinical factors	Tumour size Tumour localization Histology Biomarkers	Per protocol

Secondary 1c: bladder preservation.	Time from start of immunotherapy to the date of recurrence of muscle invasive bladder carcinoma or metastases.	Kaplan Meier estimation of survival with a 95 % confidence interval	Not applicable	Per protocol
Secondary 1d: Overall survival	Time from treatment start to exitus.	Kaplan Meier estimation of survival with a 95 % confidence interval		Per protocol
Secondary 1.3: Progression free survival	Time from treatment start to tumour relapse or distant progression.	Kaplan Meier estimation of survival with a 95 % confidence interval		Per protocol
Secondary 2: Safety profile and tolerability of combination	CTCAE V4.03	1. Frequency table with adverse events, grades and relationship to study drugs and to radiotherapy treatment 2. Frequency table with severe toxicity.	Durvalumab cumulative dose, tremelimumab cumulative dose, radiotherapy treatment constraints (dose in risk organs).	Safety population
Secondary 3: To evaluate the long term functionalism and late sequel of the treatment in the preserved bladders.	Bladder control scale	Repeated measures analysis		Per protocol
Exploratory 1: Biomarkers and pathological response rate	Biomarkers and pathological response rate	Logistic regression in which response or not is the response and baseline biomarkers are factors to be studied	Biomarkers	Per protocol

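### The Simon rule is assigned to a per-protocol set while early stoppers are replaced, yet its cut-offs are set on patients treated; unreconciled, this can add to the type I error, though the SAP suggests the final denominator was not affected

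*Combined protocol and SAP*

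**What the plan says.** **Analysis set.** Protocol 11.1.2: "The efficacy analysis set will include all patients who receive at least 2 cycles of durvalumab and 3 weeks of radiotherapy". This set is primary for efficacy. The same section adds an intention-to-treat analysis. In Table 8 (11.2.2) the primary row lists the "Simon two stage decision rule" with per protocol as its population. No decision rule is attached to the intention-to-treat analysis.

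**Cut-offs.** Section 11.2.3 places the interim look after the first twelve treated patients and asks for six or more responses. Section 11.3 asks for 19 responses among 32 treated patients.

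**Replacement.** Section 6 plans to "replace those patients who interrupt the trial in advance (without having completed 12 weeks of treatment) and have not presented dose-limiting toxicity". It adds that patients off study drug for more than 21 days, or those "who discontinue treatment with radiotherapy for more than 2 weeks will also be replaced". Section 6.1.2 repeats both rules ("It is planned to replace those patients who interrupt the trial in advance"). Only dose-limiting toxicity (DLT) is exempt, and only from the 12-week rule. Reasons to stop in 4.4 include "Confirmation of PD and investigator determination that the patient is no longer benefiting from treatment", and reasons to leave the study in 4.5 include "Death of the patient".

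**Radiotherapy gaps.** Section 6.1.1: "Patients who, for reasons unrelated to toxicity, discontinue radiotherapy for more than 2 weeks will be excluded from the study". The replacement paragraph makes no distinction by cause.

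**SAP.** Section 2.2 defines the safety set as everyone with at least one dose and keeps per protocol as the primary efficacy set. Section 3.1 runs all efficacy analyses on the safety population, because all 32 patients meet both definitions.

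**The concern.** The trial has one arm, a fixed 50% null and a decision based on a responder count. In that setting, the choice of who is counted directly affects the error rate. Two statisticians could build different denominators from this protocol, at stage 1 and at the end.

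A patient who dies or progresses early is unlikely to be a responder, and the 12-week rule allows that patient to be replaced. If the replaced patient also leaves the counted set, the response rate among those counted exceeds the rate among all treated, and a regimen no better than 50% passes more often.

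**Working it through.** **1. The plan's own figure.** Inputs from 11.3 and the synopsis: p0 = 0.5, p1 = 0.7, one-sided alpha 0.10, power 80%, n1 = 12, N = 32. With continuation at a1 or more responses and success at a or more,

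P(positive) = sum over x = a1..12 of P(Bin(12,p) = x) × P(Bin(20,p) ≥ a − x).

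A search for the Simon optimal design returns 12 + 20 = 32 with limits 6 and 19, meaning continue if more than 6 and positive if more than 19. So:

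- At least 7/12 and 20/32: type I error 0.0899, power 0.805.
- At least 6/12 and 19/32, as the protocol words them: type I error 0.1746, power 0.909.

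The sample size reproduces; the worded cut-offs do not meet 0.10. Both rules are carried forward so that the population effect can be seen separately.

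**2. Replacement and per-protocol status are different criteria.**

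- Two durvalumab cycles and three weeks of radiotherapy, then a stop before week 12 without DLT: replaced, yet still per protocol.
- DLT after one cycle: not replaced under the 12-week rule, yet outside the per-protocol set. A smaller set with fixed cut-offs lowers type I error. The 21-day rule has no DLT exemption, and how it interacts with the first rule is not stated.
- Radiotherapy gap over two weeks because of toxicity: replaced under section 6, not excluded under 6.1.1.
- The same gap for another reason: excluded from the study under 6.1.1, even if the per-protocol threshold is met.

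**3. Replaced patients leave the set.** Assume k of 32 + k dosed patients are replaced, the true rate among all dosed is 0.5, and the replaced respond at rate g. With q = k/(32 + k), the rate among those counted is p = (0.5 − q·g)/(1 − q). For g = 0 this is 0.5 × (32 + k)/32: 0.5156, 0.5313 and 0.5469 for k = 1, 2, 3. Type I error:

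| k replaced | ≥7/12, ≥20/32; g = 0 | ≥7/12, ≥20/32; g = 0.25 | ≥6/12, ≥19/32; g = 0 |
|---|---|---|---|
| 0 | 0.090 | 0.090 | 0.175 |
| 1 | 0.121 | 0.105 | 0.223 |
| 2 | 0.159 | 0.121 | 0.279 |
| 3 | 0.204 | 0.139 | 0.340 |

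If g = 0.5, nothing changes.

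**4. The set is not 32 and the cut-offs stay fixed** (≥7/12, ≥20). At n = 33 and 34 type I error is 0.117 and 0.147. This needs a replaced patient to remain per protocol, because the planned total is 32. At n = 31 and 30 it is 0.066 and 0.045, and power at 70% falls to 0.761 and 0.699.

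**5. Stage 1.** With the worded ≥6/12 and a true rate of 50%, the chance of continuing is 0.613. It becomes 0.720 or 0.811 with one or two replaced non-responders, where q = k/(12 + k). These are continuation probabilities, not false positives. Removing the stage-1 rule altogether moves type I error only from 0.090 to 0.108 (≥20/32), or from 0.175 to 0.189 (≥19/32).

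**The case against.** **The SAP largely answers the point for the final analysis.** If the safety set is everyone with a dose, and all 32 in it are per protocol, then no dosed patient lies outside the 32. The shells point the same way, though their counts are blank: Table 39 has end-of-treatment reasons other than completion, Table 45 lists patients without cystoscopy with death reason, and Table 46 keeps a row for them within its total. A reader might infer from the replacement rule that the reported response rate is inflated; the documents do not support that. But SAP 3.1 rests on observed data, SAP 2.2 still names per protocol as primary, and neither gives the stage-1 denominator or the number replaced.

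**Few patients may be affected.** Nothing in section 6 removes a replaced patient from the efficacy set, so only very early stoppers would leave it. Progression is an unlikely route: restaging CT is at week 12, and radiologic progression without clinical deterioration needs a confirmatory scan at least four weeks later. Early death or withdrawal remains possible. This limits the likely size; it does not settle who is counted.

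**Replacement is not what breaks 0.10.** A reader might infer that the plan meets 0.10 apart from replacement. It does not: the worded cut-offs give 0.175 with every treated patient counted.

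**Stage 1.** The small denominator of 12 might suggest that the main risk lies there. For type I error it does not, as step 5 shows.

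**Safeguards exist.** The intention-to-treat analysis and SAP Table 3, which lists set membership by patient, would show who was counted. Neither fixes which count decides the trial.

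**Conclusion.** The inconsistency is in the text and should be resolved. As written, the plan allows treated patients who are likely non-responders to be replaced and left out of the decisive count, which would raise type I error. One to three replaced non-responders add about 0.03 to 0.11 to a base of 0.090, or about 0.05 to 0.17 to a base of 0.175. These sizes rest on an assumed number replaced, on those patients leaving the set, and on none of them responding. With 25% response the increase on the 0.090 base is about 0.01 to 0.05; with 50% it is nil. Dropping patients without replacement works the other way and costs power.

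This is a bias that the protocol permits, not one shown to have occurred. The final denominator was probably unaffected. It is also not the only source of excess type I error, since the worded cut-offs exceed 0.10 unaided. Severity: minor to should-fix.

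**What to change.** - In Table 8, change the population for the Simon rule to patients with at least one dose: the first 12 dosed at stage 1 and the first 32 at the end. This matches the denominators in 11.2.3 and 11.3 and the population that SAP 3.1 already uses.
- State that replacement or exclusion does not remove a dosed patient from this set, and that patients dosed after the 32nd do not enter the rule.
- State under SAP Table 46 that a cystoscopy not done counts as non-response. The table keeps such patients in the total but does not say how they count.
- Report the number replaced, with reasons, and the stage-1 denominator.
- Keep per protocol as a sensitivity analysis.
- Reconcile the replacement paragraph in section 6 with 6.1.1 on radiotherapy gaps, and say what each means for the analysis sets.
- Correct the cut-off wording in the same revision and state the exact type I error of the rule used. The population change alone leaves it at 0.175 with the worded cut-offs.

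Cost: wording and a few counts, with no extra patients or procedures. The reported response rate may be slightly lower if any dosed patient had no biopsy. If no dosed patient lies outside the 32, the final denominator does not change.
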